Experimental design: This proposal seeks to elucidate the differences in reward/appeal, harshness/irritation, nicotine delivery, preference and impact of menthol flavor (compared to control tobacco flavor) between nicotine salt vs free base nicotine e-liquids. Thirty adult menthol smokers (15 male; 15 female) will participate in a double-blind, randomized, cross-over study across three experimental sessions. For the first two sessions, each participant will be randomly assigned to receive nicotine salt or freebase nicotine (both in a concentration of 36mg/ml) on two separate days (see Table 1). Freebase nicotine e-liquid at concentration of 36mg/ml has been used previously in

smokers with no reported adverse effects^{53,54} and this concentration is within range of nicotine concentrations used in nicotine salt e-liquids/e-cigarette pod devices^{55,56}. Following overnight abstinence from combustible tobacco products (CO≤10 ppm), participants will be exposed to the assigned form of nicotine in combination with two flavor conditions (tobacco and menthol) in a counterbalanced randomized order. Each exposure will consist of 2 2-sec puffs and will be separated by a 60-minute washout period (see Table 2).

iSaliva nicotine/ cotinine is an exploratory outcome and nicotine/cotinine levels will be assessed using saliva samples obtained 10 times per session (5 min prior to and 5, 15, 30, 45, and 55 minutes after the onset of puff1, and 5, 15, 30, and 45 minutes after the onset of puff2). Assessing the nicotine/cotinine levels will determine if there are pharmacokinetic differences between nicotine salts vs freebase nicotine. After completing the first two e-cigarette exposure sessions, the same thirty adult menthol smokers (15 female, 15 male) will undergo overnight abstinence from combustible tobacco and nicotine products and participant in a 60-minute choice e-cigarette self-administration session.

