1. General Labeled Magnitude Scale (gLMS)(experimental sessions)¹: For TCORS Menthol pilot, gLMS ratings will be obtained 5, 15, 30, 45, and 55 minutes after each puff during lab 1 and lab 2. Participants will rate coolness, irritation/harshness, cigarette and e-cigarette craving using the gLMS which is a category ratio scale with 7 semantic labels: "no sensation", "barely detectable", "weak", "moderate", "strong", "very strong", and "strongest imaginable". The labels are positioned quasi-logarithmically according to their empirically determined semantic magnitudes. The gLMS will be displayed on a monitor via a custom LabView® program, and participants will make their ratings using a mouse. Ratings are numerically transformed and then used for statistical analyses. For the K01 metabolism study will be assess irritation/harshness, coolness, cigarette craving, e-

cig craving at baseline, 5 and 15 min after nicotine exposure during the directed puffing section of lab sessions.

2. Labeled Hedonic Scale (LHS)(experimental sessions)³ : For TCORS Menthol pilot, liking of e-cigarette taste will be assessed 5 min after each flavor exposure using the LHS scale. The LHS is a bipolar scale with "neutral" in the middle and 5 symmetrical semantic labels: "like/dislike slightly", "like/dislike moderately", "like/dislike very much", "like/dislike extremely", "most liked/disliked imaginable", positioned on the scale according to their semantic magnitude. The LHS yields ratio-level data on the magnitude of liking/disliking of sensation equivalent to that produced by magnitude estimation (ME). This scale will also be displayed on a computer screen as above and numerically transformed.

For K01 metabolism study, liking of e-cig taste will be assessed at baseline, 5 min and 15 min after nicotine exposure during the directed puffing section of lab sessions.

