Definite: Adverse event(s) will clearly be related to investigational agent(s) or other intervention

Probable: Adverse event(s) will likely be related to investigational agent(s)

Possible: Adverse event(s) may be related to investigational agent(s)

Unlikely: Adverse event(s) will doubtfully be related to investigational agent(s)

Unrelated: Adverse event(s) will clearly not be related to the investigational agent(s)

Grades of Risk:

0: No adverse event or within normal limits

1: Mild adverse event

2: Moderate adverse event

- 3: Severe adverse event resulting in hospitalization or prolongation of existing hospitalization, a persistent or significant disability/incapacity, or a congenital anomaly/birth defect
- 4: Life-threatening or disabling adverse event
- 5: Fatal adverse event

d. For multi-site studies for which the Yale PI serves as the lead investigator:

- i. How will adverse events and unanticipated problems involving risks to subjects or others be reported, reviewed and managed? *Write here*
- ii. What provisions are in place for management of interim results? *Write here*
- iii. What will the multi-site process be for protocol modifications? *Write here*

13. **Statistical Considerations:** Describe the statistical analyses that support the study design.

Data Management: This pilot study outcomes will be collected using scannable forms (Teleforms) provided by the YCSTP Administrative Core. The scanned forms will be processed through the Teleforms software and exported to a database on a secure computer. Error checking and data validation will occur weekly and any problems will be queried and resolved immediately. The PI will receive monthly data quality reports to check for completeness and accuracy of key variables, as well as rates of recruitment, retention, and follow-up.

Statistical analyses for TCORS Menthol Pilot Study: Preliminary analyses will provide an overview of the data (e.g., randomization success, outcome distribution, missingness patterns). Outcome analyses will be intent-to-treat and using mixed-effects models. These models allow for different numbers of observations per subject, use all available data, and can handle missing-at-random data. If model assumptions appear to be violated, we will transform the data or fit more flexible generalized linear or nonparametric mixed models. We will estimate effects for a larger study.

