The mixed models will include gender (female, male) as a between-subject factor, flavor (menthol, tobacco), nicotine form (salt and freebase) as within-subject factors, and measurement time (time-within-experimental session). The models will also include all possible interactions among nicotine form and flavor and adjust for the stratification variables (sex). We anticipate significant main effects of flavor on liking/wanting of drug effects and e-cigarette taste. In addition, we expect significant main effects of nicotine form on irritation/harshness. Similar models will be used for secondary outcomes (nicotine-induced stimulation, craving and withdrawal).

Statistical Analysis for K01 Metabolism Study: Preliminary analyses will provide an overview of the data (e.g., randomization success, outcome distribution, missingness patterns). Outcome analyses will be intent-to-treat and using mixed-effects models. These models allow for different numbers of observations per subject, use all available data, and can handle missing-at-random data. If model assumptions appear to be violated, we will transform the data or fit more flexible generalized linear or nonparametric mixed models. Aim 1 and Aim 2: The mixed models will include baseline NMR (continuous), time within lab (within-subject factor), flavor (menthol, tobacco; within-subject factor), their three-way interaction, all corresponding two-way interactions and main effects. The model will also adjust for the between-subject factor sex (female, male). We will use Bayesian information criterion (BIC) to select the best fitting correlation structure for the repeated measures within subject. We will use graphical methods and polynomial terms to investigate whether the relationship between NMR and outcomes is linear. Statistical training and support will be provided by my co-mentor [name] who served as the Lead Biostatistician for Yale TCORS 1.0 and currently for Yale TCORS 2.0. She has also led statistical analysis efforts on similar experimental e-cig projects through the Yale TCORS⁶¹. **Power Analysis:** With 85

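### The TCORS cross-over model has no lab-session (period) term, although nicotine form changes only between lab 1 and lab 2

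*Combined protocol and SAP*

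**What the plan says.** Section I.4 (TCORS, Experimental design) describes a randomized cross-over. In labs 1 and 2, "each participant will be randomly assigned to receive nicotine salt or freebase nicotine (both in a concentration of 36mg/ml) on two separate days", and within each day "participants will be exposed to the assigned form of nicotine in combination with two flavor conditions (tobacco and menthol) in a counterbalanced randomized order". Counterbalancing is stated for flavor order and not for form order. On spacing within a day: "Each exposure will consist of 2 2-sec puffs and will be separated by a 60-minute washout period".

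The Assessments part of Section I.4 sets the rating times: "gLMS ratings will be obtained 5, 15, 30, 45, and 55 minutes after each puff during lab 1 and lab 2". Taste liking on the Labeled Hedonic Scale (LHS) is rated once per exposure, at 5 minutes.

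Section I.13 gives the model. Gender is the between-subject factor, followed by "flavor (menthol, tobacco), nicotine form (salt and freebase) as within-subject factors, and measurement time (time-within-experimental session"). It continues: "The models will also include all possible interactions among nicotine form and flavor and adjust for the stratification variables (sex"). It also says: "Similar models will be used for secondary outcomes (nicotine-induced stimulation, craving and withdrawal"). The stated purpose is: "We will estimate effects for a larger study". No lab-session, period or sequence term appears there or elsewhere for TCORS.

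**The concern.** In a two-period cross-over, the effect of being in period 1 or period 2 is normally a fixed effect. Here form is tied to the day, so a general shift between lab 1 and lab 2 (familiarity with the device or the rating task, for example) enters every within-person form difference with a sign set by that person's order. The listed time term cannot absorb it, because both days share the same within-session time codes.

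Two things are at stake. The residual variance and standard errors passed to the larger study would be inflated. And if form order is not balanced, part of the shift would be added to the estimated form effect.

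**Working it through.** The plan states no alpha, power or variance for TCORS, so there is no figure to reproduce. The shift sizes, the random-intercept structure and the 5% two-sided level below are assumptions.

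**Inputs.** n = 30 completers (Section III.1). Four exposures per person, 2 forms × 2 flavors (Section I.4, Table 1). Residual SD set to 1, one value per exposure. Assumed lab 1 to lab 2 shift r = 0.5 (1.0) residual SD.

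**1. Is the added term estimable?** Yes. With subject, form, flavor, form × flavor, session and exposure position, over the 8 possible orderings, the design matrix has full rank (13 of 13).

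**2. Residual variance.** Observations 120, less 30 person effects, less 3 treatment terms, leave 87 df = 3(n − 1). A shift coded ±r/2 over four cells adds r² per person to the sum of squares. With balanced form order none of it is absorbed, so residual variance = 1 + n r²/[3(n − 1)].
- r = 0.5: 1 + 30 × 0.25/87 = 1.086, about 9% too large.
- r = 1.0: 1 + 30 × 1/87 = 1.345, about 34% too large.

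**3. Reported standard error.** √1.086 = 1.042 and √1.345 = 1.160. Simulating the session shift alone, with form order balanced or simply randomized, gave ratios (term omitted / term included) of about 1.02–1.04 (1.13–1.16) over the form main effect, form within menthol, and form × flavor. With all five ratings per exposure and one omitted shift the excess is 2–3% (11–12%).

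**4. Unbalanced form order.** With n₁ and n₂ people in the two form orders, the form effect moves by r(n₁ − n₂)/n.
- 18/12: 6/30 = 0.20 × shift, or 0.10 (0.20) SD. The standard error of salt minus freebase within menthol is √(2/30) = 0.258 SD, so this is 0.39 (0.77) of a standard error.
- 20/10: 10/30 = 0.33 × shift.
- If allocation were simple randomization, binomial(30, 0.5) gives 36% for 18/12 or worse and 10% for 20/10 or worse.

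The form × flavor estimate is not moved at all, because the session shift cancels between the two flavors given on the same day.

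**5. Type I error with the term omitted.** With balanced form order it is about 4% (2%), slightly conservative. Under simple randomization, compare the true SD of each estimate with its reported standard error (87 df, critical value 1.988):

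| Contrast | True SD / reported SE | r = 0.5 | r = 1.0 | Type I error |
|---|---|---|---|---|
| Form × flavor | 1/√(1 + r²/3) | 0.96 | 0.87 | 4% (2–3%) |
| Form within menthol | √[(2 + r²)/(2 + 2r²/3)] | 1.02 | 1.06 | 5% (6–7%) |
| Form main effect | √[(1 + r²)/(1 + r²/3)] | 1.07 | 1.22 | 6–7% (10–11%) |

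Ranges cover the formula and the simulation. With the session term, simulated error stays at about 5%.

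**6. Exposure order within a day.** If time is a factor over the whole session, the ten rating times (five after each of two exposures) separate first from second exposure, and the order loss is 0. If time is minutes since each puff, both exposures share the same five codes and order is not modelled. For the LHS, minutes since the puff is constant.

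**The case against.** Flavor order is counterbalanced and form order is randomized, both labs start after overnight abstinence with the same CO limit, and nothing in the documents points to a lab 1/lab 2 shift, least of all one of 1.0 SD. A 0.5 SD shift costs only a few percent in standard error. The reference to sex as a stratification variable, with lists generated by the study biostatisticians (Section II.B.4), suggests restricted allocation, in which case the imbalance probabilities are too pessimistic. All of this stands and sets the low weight. It does not supply the missing term, and blocking of form order is not stated. The planned check of randomization success could reveal an imbalance but would not adjust for it.

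A reader might infer more than the text supports:

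- That exposure order is left out as well. The protocol uses session for a lab day containing both exposures (Section I.4, Table 2), so time within session most naturally spans both. Order is lost only under minutes-since-puff coding.
- That the form effect is confounded with day. It is not; order is randomized within the cross-over.
- That the interaction is missing. Form × flavor is in the model and matches the irritation hypothesis directly. Only the reward hypothesis in Section I.1 has two readings, and both can be estimated from the same fit.
- That false positives are generally inflated. For an omitted session shift, the two contrasts that bear on the Primary Aim stay at about 2–7%. The 10–11% figure needs a 1.0 SD shift, simple randomization and the form main effect.
- That flavor order is not recorded. The envelopes in Section II.B.4 hold the flavor randomization for each session. Since both flavors are given every session, that can only mean their order.

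**Conclusion.** The omission is real and minor. Contrasts are unbiased in expectation, but an unmodelled lab 1/lab 2 shift of 0.5 (1.0) residual SD would widen reported standard errors by about 2–4% (13–16%) and overstate the residual variance by about 9% (34%). Required sample size is proportional to variance, so a later study sized on that figure would be too large by the same percentage. If form order came out 18/12, the form effects, though not the interaction, would also move by a fifth of the shift. These sizes rest on assumed shifts, a random-intercept structure and 30 completers. The imbalance probabilities further assume simple randomization, which the documents do not state. For a pilot with no stated power target, this is an inexpensive improvement and does not threaten the conclusions.

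**What to change.** In Section I.13 (TCORS):

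- Add lab session (1/2) as a fixed effect.
- Define measurement time as a factor over the whole session, so that it also absorbs exposure order. If time is instead coded as minutes since each puff, or the outcome has one rating per exposure (LHS), add exposure order (first/second) as a fixed effect.
- State whether form order is balanced across participants.
- As a minor clarification, say whether the reward hypothesis is tested by salt-menthol minus freebase-menthol or by form × flavor. With n = 30 their standard errors are √(2/30) = 0.258 and √(4/30) = 0.365 residual SD, so the choice matters for precision and should be made before the data are seen.

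The cost is a few sentences and 1 or 2 residual df (87 to 86 or 85 with one value per exposure). Session is on the pod labels and flavor order is in the randomization envelopes (Section II.B.4), so no new data collection is needed.

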Secondary Aim: Examine the influence of menthol flavor on the effects of nicotine (freebase vs salt) stimulation, craving reduction, and alleviation of nicotine withdrawal. Participants will rate nicotine withdrawal and stimulation using the Revised DEQ and cigarette craving using the gLMS.

Exploratory Aim: Examine nicotine delivery following exposure to nicotine salt vs freebase nicotine exposure in combination with flavors (tobacco or menthol) by measuring saliva nicotine levels 5 min prior and 5, 15, 30, 45, and 55 minutes after nicotine and flavor exposure via e-cigarettes

K01 metabolism study

Eighty-Five African Americans (43 F, 42 M) who smoke and have experience with e-cigarettes will participate in a double-blind, randomized, cross-over study across two experimental sessions. Following overnight abstinence from combustible tobacco products (CO≤10 ppm), participants will be randomly assigned to receive an e-cigarette with menthol flavor or control tobacco flavor (both in a concentration of 5% nicotine) on two separate days. Each session will consist of 1 puffing bout (10 puffs, 3 sec each puff, 30 sec puff interval) followed by 2 hours of abstinence, then 60 minutes of ad libitum e-cigarette use. The specific aims are:

Aim 1: Investigate the relationship of menthol flavor (vs tobacco flavor) and nicotine metabolite ratio (NMR) on nicotine pharmacokinetics and subjective effects during directed e-cigarette administration in African Americans who smoke. We hypothesize that during the menthol exposure session participants will have higher plasma nicotine levels compared to the tobacco flavor exposure session. We hypothesize that NMR is negatively associated with nicotine plasma levels during the tobacco flavor exposure sessions. Lastly, we hypothesize that participants will have a larger reduction of cigarette craving in the menthol compared to tobacco session. Primary outcomes: plasma nicotine boost, nicotine area under the curve. Secondary outcome: cigarette craving. Exploratory outcomes: other subjective effects such as liking of e-cig taste. Gender differences will be explored for all outcomes.

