Aim 2: Elucidate the relationship between menthol flavor (vs tobacco flavor) and NMR on nicotine pharmacokinetics and subjective effects during e-cigarette ad libitum use in African Americans who smoke. We hypothesize that participants will take more puffs during the menthol session compared to the tobacco session. Additionally, we hypothesize that participants will titrate their nicotine intake and have similar nicotine plasma levels for both flavor exposure sessions. Furthermore,

we hypothesize that NMR will be positively associated with nicotine delivery (amount of e-liquid used x nicotine e-liquid concentration) for both flavor sessions. Lastly, we hypothesize that participants will have a larger reduction of cigarette craving in the menthol compared to tobacco session. Primary outcomes: plasma nicotine boost, nicotine area under the curve. Secondary outcomes: measure of nicotine delivered to participant and cigarette craving. Exploratory outcomes: number of puffs and subjective effects. Gender differences will be explored for all outcomes.

2. **Probable Duration of Project:** State the expected duration of the project, including all follow-up and data analysis activities.

2 years

TCORS Menthol Pilot Study

Study	Quarter 1	Quarter 2	Quarter 3	Quarter 4
2 experiment sessions	7 completers	7 completers	8 completers Analyze results.	8 completers Analyze results. Present at conference. Publish

K01 Metabolism Study

I anticipate completing both phases of the study by the end of this 5-year K01 award (funded Sept 2020). I anticipate completing 21 participants per year.

3. **Background:** Describe the background information that led to the plan for this project. Provide references to support the expectation of obtaining useful scientific data.

TCORS Menthol Pilot Study

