Experimental Design: Aim 1 focuses on the directed e-cigarette administration procedure. Saliva NMR will be assessed at intake appointment and will be a continuous measure in this study^{59,60}. Following overnight abstinence from combustible tobacco products (CO≤10 ppm), African Americans who smoke will participate in a double-blind, counterbalanced and randomized e-cigarette exposure laboratory study where they will receive two e-liquid flavors (menthol, tobacco) with a fixed nicotine salt concentration in e-cigarettes (5%) on two separate days (one flavor condition per session). The directed e-cigarette administration procedure will consist of 1 fixed-puffing bout (puffing bout=10 puffs, 3 sec each puff, 30 sec puff interval) as done previously by my mentor, [name]. Per the procedures conducted by my co-mentor [name] research group^{62,63}, plasma nicotine levels will be assessed at baseline and 5, 15, 30, 45 and 60 minutes after nicotine exposure via e-liquids during the directed e-cigarette administration procedure. Heart rate and blood pressure will be measured at 5, 15 and 30 minutes after the final puff. Participants will rate irritation/harshness, coolness, cigarette craving, e-cigarette craving, liking of e-cig taste, reward/appeal of e-cig, nicotine withdrawal and stimulation at baseline, 5 and 15 min after nicotine concentration exposure. Participants will be told that they can stop anytime if they feel uncomfortable. **Independent variables:** sex (male or female), nicotine metabolite ratio, flavor (menthol, tobacco), **Dependent variables:** primary outcomes- plasma nicotine boost, nicotine area under the curve; secondary outcomes- cigarette craving; exploratory outcomes- reward/appeal of e-cigs, e-cig craving, irritation/harshness, coolness, nicotine withdrawal, stimulation, liking of e-cig taste. We will explore gender differences for all outcomes.

Aim 2: Elucidate the relationship between menthol flavor (vs tobacco flavor) and NMR on nicotine pharmacokinetics and subjective effects during e-cigarette ad libitum use

Eligibility/ Recruitment/Screening: African Americans who participate in Aim 1 will participate in Aim 2.

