subjects in total (43 women, 42 men) we will have 80% power at two-sided alpha level 0.05 to detect a correlation of 0.30 or bigger in absolute value between NMR and the primary study outcomes. For the within subject comparisons of the tobacco and menthol flavor sessions, with 85 individuals we will have 80% power at two-sided alpha level 0.05 to detect a medium effect size (Cohen's $d=0.32$) for the primary study outcomes. This is a cross-over study, so all 85 participants will participate in Aim 1 and Aim 2 of this K01 proposal.

SECTION II: RESEARCH INVOLVING DRUGS, BIOLOGICS, RADIOTRACERS, PLACEBOS AND DEVICES

If this section (or one of its parts, A or B) is not applicable, check off N/A and delete the rest of the section.

A. RADIOTRACERS N/A

1. Name of the radiotracer: *Write here*
2. Is the radiotracer FDA approved? YES NO

If NO, an FDA issued IND is required for the investigational use unless RDRC assumes oversight.

B. DRUGS/BIOLOGICS N/A (IND not applicable; ITP assessed)

TCORS Menthol Pilot Study

The Suorin iShare™ and available e-liquids will be used for this study. The Suorin iShare™ is a refillable pod system e-cigarette device composed of a battery without voltage control and a refillable pod that contains the e-liquid, mouthpiece and coil. It is among one of the pod e-cigarette devices that are used widely^{57,58}. We have received an ITP from the FDA to use this e-cigarette device.

The following e-liquids will be purchased from e-liquid from American eLiquid Store:

- 1) DuraSmoke® Tobacco Menthol eLiquid 36mg/ml
- 2) Tobacco - Menthol eLiquid AmericaneLiquid® 36mg/ml
- 3) DuraSmoke® Tobacco Virginia eLiquid 36mg/ml
- 4) Tobacco - Virginia Flue Cured eLiquid AmericaneLiquid® 36mg/ml

We have received documentation from the American eLiquid Store stating that the above e-liquids were on the market prior to August 2016 so we do not need an ITP for these e-liquids.

K01 Metabolism Study

The JUUL™ and JUULpods™[5%(59mg/ml)] will be used for this study. The JUUL™ is one of the most widely used pod e-cigarette devices^{57,58}. We do not need an ITP from the FDA to use this e-cigarette device and products as they predate the enforcement compliance date.

The following JUULpods will be purchased:

- 1) Menthol eLiquid 59mg/ml (5%)nicotine

2)VirginiaTobacco eLiquid 59mg/ml (5%)nicotine

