We anticipate dropout so we will recruit 60 subjects. We anticipate 60 participants to participate in the initial appointment and 42 to complete lab session 1 and 37 to complete both lab sessions. Our target for completion is 30 participants.

K01 Metabolism Study

We anticipate dropout so each year (5 years total) we will recruit 23 subjects. We anticipate 23 participants to participate in the initial appointment and 17 to complete lab session 1 and 2. Our target for completion is 85 participants.

b. If this is a multi-site study, give the total number of subjects targeted across all sites: *Write here*

2. Indicate recruitment methods below. Attach copies of any recruitment materials that will be used.

 Flyers	 Internet/web postings	 Radio
 Posters	 Mass email solicitation	 Telephone
 Letter	 Departmental/Center website	 Television
 Medical record review*	 Departmental/Center research boards	 Newspaper
 Departmental/Center newsletters	 Web-based clinical trial registries	 Clinicaltrials.gov
 YCCI Recruitment database	 Social Media (Twitter/Facebook):	
 Other:		

* Requests for medical records should be made through JDAT as described at
<http://medicine.yale.edu/ycci/oncore/availableservices/datarequests/datarequests.aspx>

3. Recruitment Procedures:

- a. Describe how potential subjects will be identified. Recruitment will be through advertisements at local colleges, in Craigslist, Facebook, YCCI Recruitment database Instagram, Twitter, Google ads and other social media platforms, radio ads, newspaper ads, novelties (e.g. coasters, matchbooks, etc.) flyers in the community(for example barbershops, hair salons, grocery stores in predominately Black communities) bus stops, within buses, word of mouth recruitment through community organizations, partnering with community groups, etc.

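### The K01 mixed model omits a session (period) term in a two-session crossover; adding it is a nearly free gain in precision

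*Combined protocol and SAP*

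**What the plan says.** Section I.4 (Experimental Design, Aim 1) describes K01 as a "double-blind, counterbalanced and randomized e-cigarette exposure laboratory study". Each participant receives menthol in one session and tobacco in the other, on separate days. Aim 2 uses the ad libitum period of the same two sessions. The power paragraph of Section I.13 also calls the study a crossover.

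Section I.13 gives one model for both aims: "The mixed models will include baseline NMR (continuous), time within lab (within-subject factor), flavor (menthol, tobacco; within-subject factor), their three-way interaction", followed by the two-way interactions, the main effects and sex. The correlation structure for the repeated measures is to be chosen by BIC. The independent variables listed under Aims 1 and 2 in Section I.4 are sex, NMR and flavor. No K01 section names session, period, order or sequence as a model term.

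The power statement for the flavor contrast reads "For the within subject comparisons of the tobacco and menthol flavor sessions, with 85 individuals we will have 80% power" at two-sided alpha 0.05 for d = 0.32.

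**The concern.** Time within lab indexes sampling times inside a session. It cannot represent a difference in level between the first and second session. Such a difference adds to the menthol-minus-tobacco difference in participants who take tobacco first and subtracts from it in those who take menthol first. Without a session term, this systematic spread is counted as random error.

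The flavor contrast carries the powered within-subject comparison and the Aim 1 hypothesis of higher plasma nicotine with menthol. What is at stake is mainly the precision of that contrast.

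**Working it through.** **Inputs from the documents (Section I.13).** n = 85, d = 0.32, two-sided alpha 0.05, stated power 80%.

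**Assumed, because the documents give neither.** The session shift p, defined as the session 2 minus session 1 mean in SDs of the paired difference, and the sequence split n1/n2 (the 43/42 in the documents is the split by sex). Each session is reduced to one value per participant.

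**1. The plan's own figure.** For a paired t test the noncentrality is 0.32 × √85 = 2.950 on 84 df, which gives power 83.1%. The plan says 80%; the effect detectable at 80% is d = 0.307. The stated power is slightly cautious. This is a separate matter and does not bear on the missing term.

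**2. With the session term.** SE = 0.5 × √(1/n1 + 1/n2) on 83 df. The shift drops out, so power does not depend on p.
- 43/42: 83.0%
- 46/39: 82.8%
- 50/35: 81.9%

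**3. Without the term, sequences near equal.** The paired difference is 0.32 + p in one sequence and 0.32 − p in the other, plus error with SD 1. The estimated variance rises to about 1 + p², while the true sampling variance of the mean stays at 1/85. The confidence interval therefore widens by about √(1 + p²), and power is approximately Φ(2.950 − 1.989 × √(1 + p²)). For p = 0.5 this is Φ(2.950 − 1.989 × 1.118) = Φ(0.73), about 0.77. Simulation, averaged over 43/42 and 42/43, gives:

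| Assumed shift p | CI wider by | Power without term | Power with term | Type I error without term |
|---|---|---|---|---|
| 0 | 0% | 83.1% | 83% | 5.0% |
| 0.2 | 2% | 82.1% | 83% | 4.5% |
| 0.32 | 5% | 80.5% | 83% | 4.0% |
| 0.5 | 12% | 76.3% | 83% | 2.9% |
| 1.0 | 42% | 55.2% | 83% | 0.6% |

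Type I error falls below 5%, so the unadjusted test is conservative. Regressing the paired difference on centred NMR, with and without session, gives the same standard-error ratios: 1.00, 1.12 and 1.42 at p = 0, 0.5 and 1.0.

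**4. Without the term, sequences unequal.** The flavor estimate moves by p × (n1 − n2)/85.
- 46/39, p = 0.5: 0.5 × 7/85 = 0.041, so 0.32 becomes 0.36 or 0.28 according to direction. Power is 86% or 64%, and type I error is 4.0%.
- 50/35, p = 0.5: 0.5 × 15/85 = 0.088, so 0.32 becomes 0.41 or 0.23. Type I error is about 8.5%.

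Both results are conditional on that split having occurred.

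**The case against.** The strongest reply is that little harm is shown. Counterbalancing protects the flavor estimate when sequences are near equal. Power is still about 80% at a shift of 0.32 SD, which is as large as the effect the study is powered to detect. The directed-puffing sessions are standardised, and participants already have e-cigarette and pod experience. If boost is a change from baseline, a stable level shift would largely cancel in it. Nothing in the documents points to a shift of 0.5 or 1.0 SD. All of this stands, and it is why the point is minor.

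Two further replies do not remove it. BIC chooses a covariance structure, which does not take a mean shift out of the flavor contrast. The planned preliminary look at randomization success and missingness may reveal unequal sequences, but it adds no term to the model.

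A reader might also infer more than the documents allow. Section III.1 says, per year, "We anticipate 23 participants to participate in the initial appointment and 17 to complete lab session 1 and 2", or 5 × 23 = 115 and 5 × 17 = 85 in all. It is tempting to read this as dropout that unbalances the sequences and biases the flavor effect. But the 23 attend intake, where eligibility is still being settled (Sections I.9 and I.11), and people who fail there have received no study flavor. So 115 is only an upper bound on the number entering the crossover, and no K01 loss between sessions 1 and 2 is given. If allocation is balanced and dropout unrelated to sequence, the chance that 85 completers split 46/39 or worse is 21% from 115 entrants, 9% from 100, 5% from 95 and nil from 90; these entry numbers are assumptions.

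**Conclusion.** The omission is real: an explicit fixed-effects list for a two-session crossover contains no session term. With near-equal sequences the consequence is lost precision and a conservative test. The loss is about 1 power point at an assumed shift of 0.2 SD, 7 at 0.5 SD and 28 at 1.0 SD (step 3), and nothing if there is no shift.

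The documents do not support a claim of expected bias or of inflated false positives. Bias requires unequal analysed sequences together with a shift, and the documents give neither a sequence allocation nor a shift size. The 8.5% type I error belongs to one extreme assumed split. The results also rest on treating each session as a single value and on participants who complete both sessions, whereas the planned model uses all available data. This is a cheap improvement of minor severity.

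**What to change.** In Section I.13, add session (1 vs 2) as a fixed effect to every K01 flavor model for Aims 1 and 2, and report the numbers analysed by sequence.

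The cost is one degree of freedom. With no shift, power goes from 83.1% to 83.0% at 43/42 and 82.8% at 46/39, a loss of 0.0 to 0.3 points on unrounded figures, and to 81.9% at 50/35, about 1 point. The sample size stands. No new data are needed, because the flavor assigned to each session is already held in the participant envelopes (Section II, Storage, Preparation and Use). The term should be written into the plan before the data are examined, so that it is not a choice made after seeing them.
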